## Clinical Investigation Plan

7. Subject is willing and able to comply with the prescribed follow-up evaluations

### 5.3.1.2 Exclusion Criteria

1. Subject is currently participating in another clinical investigation that may confound the results of this study
2. Ongoing systemic or local infection in the area of the procedure
3. Recent use of anticoagulants or subject with coagulopathy
4. Primary complaint of deafferentation pain
5. Presence of other anatomic or comorbid conditions, or other medical, social, or psychological conditions that, in the investigator's opinion, could limit the subject's ability to participate in the clinical investigation or to comply with follow-up requirements of the clinical investigation results
6. Subject's opioid usage is > 90 morphine equivalents per day

### 5.3.2 Candidate subjects with facet joint pain (lumbar or cervical)

#### 5.3.2.1 Inclusion criteria

1. Subject has unilateral or bilateral pain on para-spinal palpation and localized pain with extension/lateral bending
2. Subject has facet joint pain confirmed by at least 1 positive medial branch block with 0.5 mL or less of anesthetics (across at least 3 vertebral levels) achieving at least 50% pain relief, with real-time injection of radiographic contrast under fluoroscopic guidance (adapted from the consensus practice guidelines; Cohen et al)

### 5.3.3 Candidate subjects with sacroiliac joint pain

#### 5.3.3.1 Inclusion criteria

1. Subject has sacroiliac joint pain based on medical history and physical exam
2. Subject has sacroiliac joint pain confirmed by an infiltration of local anesthetics in the posterior part of the sacroiliac joint achieving at least 50% pain relief

### 5.3.4 Candidate subjects with radicular pain

#### 5.3.4.1 Inclusion criteria

1. Subject has radicular pain based on medical history and physical exam
2. Subject has radicular pain confirmed by dermatomal mapping corresponding to at least 1 nerve root level

### 5.3.5 Candidate subjects with trigeminal neuralgia

#### 5.3.5.1 Inclusion criteria

1. Subject has trigeminal pain based on medical history and physical exam
2. Subject did not have any mass effect or stroke causing trigeminal pain confirmed by MRI
3. Subject is ≥ 60 years of age in case of a neurovascular conflict

## Clinical Investigation Plan

### 5.3.5.2 Exclusion criteria

1. Subject has sensory problems

### 5.3.6 Candidate subjects with knee or hip pain

#### 5.3.6.1 Inclusion criteria

1. Subject has knee or hip pain based on medical history and physical exam
2. Subject has radiographically confirmed osteoarthritis of the hip or knee, or has chronic pain following joint arthroplasty

## 5.4 Subject Enrollment

A subject is considered enrolled in the clinical investigation when the following conditions are met:

1. Subject has provided written informed consent
2. Subject has been determined to meet all Inclusion/Exclusion requirements

## 5.5 Subject Deregistration

Subjects are considered deregistered if the RFA procedure was not performed for any reason (e.g., payor denial), and are excluded from the Full Analysis Set (FAS). [REDACTED] Deregistered subjects, although excluded from the FAS, must be followed and documented according to the CIP requirements until they are withdrawn. Subjects who are deregistered for the above-mentioned reasons will not count towards the total sample size.

## 5.6 Subject Withdrawal and Discontinuation

Each enrolled subject shall remain in the clinical investigation until completion of the required follow-up period; however, a subject's participation in any clinical investigation is voluntary and the subject has the right to withdraw at any time without penalty or loss of benefit. Conceivable reasons for discontinuation may include, but not be limited to, the following:

- Subject death (cause must be documented)
- Subject voluntary withdrawal
- Subject lost-to follow-up as described below
- Subject's follow-up is terminated by the Sponsor (per Section 3.3)
- Subject deregistration (per Section 5.5)
- Subject receives additional chronic pain treatment (neuromodulation implant or other) for the same anatomical region during the follow-up period

The Sponsor must be notified of the reason(s) for subject discontinuation. The site will provide this information to the Sponsor. Investigators must also report this to their respective IRB/EC as defined by their institution's procedure(s).

No additional follow-up will be required or data recorded from subjects once withdrawn from the clinical investigation.

## Clinical Investigation Plan

However, if a subject withdraws from the investigation due to problems related to the safety or performance of the device under investigation, the investigator shall ask for the subject's permission to follow his/her status/condition outside of the clinical investigation.

### Lost-to-Follow-up

If the subject misses two scheduled follow-up time points and the attempts at contacting the subject detailed below are unsuccessful, then the subject is considered lost-to-follow-up. Site personnel shall make all reasonable efforts to locate and communicate with the subject (and document these efforts in the source documents), including the following, at each contact time point:

- A minimum of two telephone calls on different days over the specified follow-up windows to contact the subject should be recorded in the source documentation, including date, time and initials of site personnel trying to make contact.
- If these attempts are unsuccessful, a letter (certified if applicable) should be sent to the subject.
- If a subject misses one follow-up contact time point, it will be considered a missed visit. The subject may then return for the subsequent visit (if applicable). If the subject misses two consecutive time points and the above-mentioned attempts at communicating with the subject are unsuccessful, the subject will be considered lost-to-follow-up.

Telephone contact with General Practitioner or relative without the presence of the subject or indirect documentation obtained via discharge letters will not be considered as subject contact.

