## Clinical Investigation Plan

### 3.1 Clinical Investigation Procedures and Follow-up Schedule

The flowchart and the follow-up requirements of this clinical investigation are described below.

**Figure 2.** Clinical Investigation Flowchart

Clinical sites will follow subjects until the last subject completes their 6-month visit.

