### 6.4 Follow-up Assessments

#### 6.4.1 Follow-up for All Subjects

Follow-up visits will occur at 3 and 6 months ( $\pm$  30 days) after the (last) RFA procedure.

The following data will be collected at each visit:

- Occupational and lifestyle information
- NRS score

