## Clinical Investigation Plan

### APPENDIX IX: CIP SUMMARY

Clinical Investigation Name and Number	ROSTRA (CRD_1029)
Title	Real-World Outcomes Study on Subjects Treated with Radiofrequency Ablation
Objective	The objective of this study is to collect real-world safety and effectiveness data on Abbott's IonicRF™ Generator and compatible RFA accessories. This post-market study is intended to satisfy EU MDR requirements.
Device Under Investigation	IonicRF Radiofrequency Generator, along with any country-specific market-released accessory (i.e. electrode, cannula, grounding pad, and adaptor cable) compatible with the IonicRF Generator.
Number of Subjects Required for Inclusion in Clinical Investigation	The study will enroll up to [REDACTED] patients at up to [REDACTED] sites in Europe and the US. Additional centers may be approached for participation in the study as needed.
Clinical Investigation Design	International, prospective, non-randomized, single-arm, multi-center, and post-market study
Primary Endpoints	
The primary effectiveness endpoint is the relative change in Numeric Rating Scale (NRS) [REDACTED] follow-up visit. NRS is the patient's self-rating of average pain intensity for the area being treated over [REDACTED] from 0 "no pain" to 10 "worst pain imaginable". This will be calculated for each represented indication.
 
The primary safety endpoint is the incidence of device- and procedure-related serious adverse events.

Subject Follow-up	Follow-up visit: Subjects will be followed at 3 and 6 months from the date of (last) RFA procedure
Inclusion Criteria for all candidate subjects	
 
1. Subject must provide written informed consent prior to any clinical investigation-related procedure
 
2. Subject is <math>\geq</math> 18 years of age
 
3. Subject has chronic pain <math>></math> 6 months and was unresponsive to conservative management
 
4. Subject has pain on an NRS scale of <math>\geq</math> 6
 
5. Subject is scheduled for an RFA procedure with the IonicRF generator within 30 days of baseline to treat chronic pain at one anatomical region
 
6. Subject has stable chronic pain medication use for 30 days
 
7. Subject is willing and able to comply with the prescribed follow-up evaluations
 

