3.2 Adverse Events

All deaths, serious adverse events related to device/procedure (SADE) and non-serious adverse event related to device/procedure (ADE) will be summarized for FAS population excluding deregistered patients, as frequency, proportion, and number of events per patient years of follow up.

3.3 **Subject Early Termination**

Subject early termination reasons including deaths, voluntary withdrawal, lost-to-follow-up, deregistration, receiving additional chronic pain treatment for the same anatomical region during the follow-up period, etc. will be summarized at all scheduled visits.

3.4 **Protocol Deviation**

Protocol deviations will be summarized by major and minor categories for subjects in whom a protocol deviation was reported.

3.5 **Descriptive Endpoints or Additional Data**

The following descriptive endpoints will be reported using summary statistics.

- 1. The following will be characterized at RFA procedure(s):
 - Overall procedure and RF time
 - A summary of Abbott RFA accessory model numbers used in the procedure
- 2. The following will be characterized at follow-up visits:
 - Patient reported (%) pain relief
 - Patient satisfaction
 - Patient Global Impression of Change (PGIC): to evaluate the subject's impression of change in his/her condition since the beginning of the study treatment
 - Device- and procedure-related adverse events
 - Device deficiencies
- 3. Change from baseline to each follow-up visit in
 - NRS (raw change); the raw change is defined as (Baseline NRS score
 – Follow-up NRS score)
 - EQ-5D quality of life survey, consisting of a descriptive system and the EQ VAS. The descriptive system comprises five dimensions: mobility, self-care, usual activities, pain/discomfort, and anxiety/depression. The EQ VAS records the patient's self-rated health on a vertical visual analogue scale

- PROMIS-29 assesses pain intensity using a single 0-10 numeric rating item and eight health domains (physical function, fatigue, pain interference, depressive symptoms, anxiety, ability to participate in social roles and activities, cognitive function/abilities, and sleep disturbance) using four items per domain
- Opioid medication usage
- Oswestry Disability Index (ODI): 10-item scale that evaluates disability related to low-back pain (only for back pain patients)
- Neck Disability index (NDI): 10-item scale that evaluates disability related to neck pain (only for neck pain patients)

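### Lost to follow-up needs two missed time points in a study with only two, so a subject who vanishes after month 3 can never be classed as lost and that row of the SAP 3.3 summary is understated

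*Protocol*

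**What the plan says.** The Lost-to-Follow-up part of Protocol 5.6 gives the definition twice. The opening sentence sets the condition "If the subject misses two scheduled follow-up time points", together with failed contact attempts. The last bullet repeats it with the misses in sequence: "If the subject misses two consecutive time points and the above-mentioned attempts at communicating with the subject are unsuccessful". In between, a single miss gets a different status: "If a subject misses one follow-up contact time point, it will be considered a missed visit". The subject may then come back for the next visit, where there is one.

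Protocol 6.4.1 sets the schedule: "Follow-up visits will occur at 3 and 6 months". The Schedule of Events (6.5.1) shows the same two visits plus an unscheduled column, and Appendix IX agrees: "Subjects will be followed at 3 and 6 months from the date of (last) RFA procedure". Protocol 3.1 describes when site follow-up ends ("Clinical sites will follow subjects until the last subject completes their 6-month visit") but adds no later visit.

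SAP 3.3 says what is reported. It summarizes "Subject early termination reasons including deaths, voluntary withdrawal, lost-to-follow-up" and further reasons at all scheduled visits.

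**The concern.** A rule that needs two misses works when there are enough visits for a subject to attend some, disappear, and then miss two. Here there are only two visits. Attending the first uses up one of the two misses that the definition requires. The only subjects who can be classed as lost are those never seen at a scheduled visit after treatment, and they qualify only once the month-6 visit has also been missed.

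At stake is the meaning of one row in a table that the SAP commits to. The study is single-arm and unblinded, and its effectiveness analyses use available data, so the reasons for absence at month 6 matter to a reader. Missed visit does not separate someone who skipped an appointment from someone who disappeared.

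**Working it through.** **Inputs.** Definition: two missed time points, consecutive in the second statement, plus failed contact (Protocol 5.6). Scheduled follow-up visits: two (Protocol 6.4.1, 6.5.1, Appendix IX; the times in section 3.0 are redacted). Unscheduled visits are not scheduled time points. Number of subjects: 180 (Protocol 5.7). The readable text states no attrition rate, and the sample-size sections are redacted, so there is no plan figure to reproduce.

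**Step 1: apply the rule to every attendance pattern**, taking contact attempts after a missed visit to have failed.

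| Month 3 | Month 6 | Missed | Status under Protocol 5.6 | Month-6 data |
|---|---|---|---|---|
| attended | attended | 0 | complete | present |
| attended | missed | 1 | missed visit | absent |
| missed | attended | 1 | missed visit | present |
| missed | missed | 2 | lost to follow-up | absent |

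Two patterns lack month-6 data, and only one of them can be classed as lost. The second and third rows get the same status, although one subject has vanished and the other came back. The word consecutive makes no difference, because two misses out of two visits are always consecutive. At month 3 nobody can yet meet the definition, so the lost count there is zero by construction.

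**Step 2: illustrate the size.** Let a be the share of all subjects who silently vanish before month 3, and b the share of all subjects who do so between months 3 and 6. These rates are assumptions. Silent means not recorded as death, withdrawal or re-treatment.

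- Counted as lost by the rule: 180 × a
- Vanished in total: 180 × (a + b)
- Share not labelled lost: b / (a + b)
- Subjects with month-6 data, under either definition: 180 × (1 − a − b), if there is no other missingness

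| a | b | Counted as lost | Vanished | Share not labelled | With month-6 data |
|---|---|---|---|---|---|
| 2% | 2% | 3.6 | 7.2 | 50% | 172.8 |
| 5% | 5% | 9 | 18 | 50% | 162 |
| 10% | 10% | 18 | 36 | 50% | 144 |
| 10% | 2% | 18 | 21.6 | 17% | 158.4 |
| 2% | 10% | 3.6 | 21.6 | 83% | 158.4 |

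Across this range the rule counts about 4 to 18 of about 7 to 36 vanished subjects. The share left unlabelled runs from 17% to 83%, depending on when the losses fall.

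**Step 3: what the label does not change.** The last column is the same under either definition. Effectiveness analyses use available data (Protocol 8.6, SAP 2.9), so the estimate does not move.

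**The case against.** The strongest reply is that this is a labelling matter with little effect on what a reader can learn. Most of its parts stand.

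- SAP 3.3 also covers deaths, voluntary withdrawal, deregistration and further pain treatment, and its list is open-ended. The list in Protocol 5.6 is open too, and the Schedule of Events has a withdrawal entry at month 6. A site could record a vanished subject under another reason.
- SAP 2.2.1 reports numbers of observations for continuous outcomes, change in NRS among them. Missing month-6 data will show whatever the status is called.
- Protocol 8.6 allows a sensitivity analysis with imputation for patient-reported outcomes, although only as an option.
- Protocol 5.6 qualifies the return to a later visit as applying only where there is one, so the text allows for a missed final visit.

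This limits the consequences but does not remove the gap. The qualifier leaves the vanished subject as a missed visit, which is the problem. The open lists permit another reason but do not require one, so sites may code the same event differently.

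A reader might infer three stronger things. First, that reported attrition as a whole is too low: the documents state no attrition figure, and only the lost-to-follow-up row is affected. Second, that every loss after month 3 disappears from the table: only silent non-contact does. Third, that the primary effectiveness result is biased by the rule: the label leaves the estimate unchanged. The visit for the primary endpoint is redacted, as is part of the SAP 2.9 sentence on discontinuation, so nothing can be said about whether losses after month 3 reach that endpoint.

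**Conclusion.** The definition and the schedule do not fit together. An unreachable subject who attended month 3 cannot be classed as lost to follow-up, so that row of the SAP 3.3 summary is understated by construction whenever such losses occur. This follows from the text and needs no assumption beyond the two-visit schedule.

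The size is unknown. The illustrative range rests on 180 subjects and on assumed silent losses of 2% to 10% of all subjects in each period; it is not a forecast. The point concerns how losses are classified and reported. It does not show a bias in an estimate or an error in the month-6 number of observations. It is worth correcting because the plan states a rule that miscounts something it intends to tabulate, and the correction is small.

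**What to change.** Amend the Lost-to-Follow-up text in Protocol 5.6 so that a subject is classed as lost when the 6-month visit is not done within its window and the listed contact attempts have failed, whether or not month 3 was attended. Date the loss at the last actual contact. Keep missed visit for a missed month 3 followed by an attended month 6. Use the same status in SAP 3.3.

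SAP 2.2.3 needs no change: it already censors at the last known event-free time point, which does not depend on this status.

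The cost is one sentence in the Protocol, a status code on the case report form and matching wording in the SAP. No visits or contact attempts are added, because Protocol 5.6 already requires the attempts at each time point. The downside for the sponsor is that the reported lost-to-follow-up count becomes less favourable. The change is best made before database lock, while sites can still code these subjects uniformly.

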### 5.7 Number of Subjects

180 subjects

### 5.8 Total Expected Duration of the Clinical Investigation

[REDACTED]

### 6.0 TREATMENT AND EVALUATION OF ENDPOINTS

#### 6.1 Enrollment

During Enrollment, the following procedures will be performed:

- Verification of written informed consent
- Inclusion/Exclusion eligibility

#### 6.2 Baseline

Baseline assessments should be completed on the same day of enrollment and after the diagnostic block(s) and/or other evaluations to determine if a subject qualifies for an RFA procedure. The diagnostic block should only be used as a diagnostic tool and its therapeutic effect should be completely nullified at the time of the baseline assessment.

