## 4.0 ENDPOINTS

### 4.1 Primary Effectiveness and Safety Endpoint

The primary effectiveness endpoint is the relative change in Numeric Rating Scale (NRS) [REDACTED] [REDACTED] follow-up visit. NRS is the patient's self-rating of average pain intensity for the area being treated over [REDACTED] from 0 "no pain" to 10 "worst pain imaginable". This will be calculated for each represented indication.

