## 5.3 Eligibility Criteria

Assessment for eligibility criteria is based on medical records of the site and interview with a candidate patient. Patients must meet ALL general inclusion criteria and the inclusion criteria specific to the patient's chronic pain indication to participate in the clinical investigation. If ANY general exclusion criteria or exclusion criteria specific to the patient's chronic pain indication (if applicable) are met, the patient is excluded from the clinical investigation and cannot be enrolled.

If any clinical tests are required for patient screening and are not included in a site's standard tests, they must be completed after written informed consent is obtained.

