## Clinical Investigation Plan

### 6.2.1 Baseline Clinical Assessments

The following data will be recorded at baseline:

- Subject demographics
- Occupational and lifestyle information
- Subject medical history (pain history and other interventions for pain management)
- Subject pain diagnosis and pain location
- NRS score
- EQ-5D-5L
- PROMIS-29
- Opioid medication usage
- ODI (only for subjects with back pain)
- NDI (only for subjects with neck pain)
- WOMAC index score (only for subjects with knee and hip pain)
- Serious adverse events resulting in death (if applicable)

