#### 6.4.2.1 Numerical Rating Scale (NRS)

All subjects should answer the NRS question. The pain NRS consists of 1 question that will be asked by interviewing the subjects. Patients will be asked to rate, from 0 (no pain) to 10 (worst imaginable pain), their average pain over the past 24 hours specific to the area(s) of chronic pain being treated. A higher score indicates greater pain intensity.

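### The diagnostic-block rule covers only the moment of the baseline assessment, while the baseline NRS averages the previous 24 hours, so a compliant baseline can include hours of block relief

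*Protocol*

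**What the plan says.** Protocol section 6.2 places the baseline assessments after any diagnostic block and on the day of enrollment. It treats the block purely as a diagnostic tool and adds that "its therapeutic effect should be completely nullified at the time of the baseline assessment".

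Protocol section 6.4.2.1 has subjects rate "their average pain over the past 24 hours specific to the area(s) of chronic pain being treated". The recall period is blacked out in section 4.1, so the 24 hours is taken from 6.4.2.1. Section 6.2.1 and the schedule of events both list the NRS at baseline.

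The primary effectiveness endpoint (protocol 4.1, SAP 1.4.2) is the relative change in NRS, calculated for each indication. The responder endpoints (protocol 4.2, SAP 3.5) are decreases of at least 30% and at least 50% on the same scale.

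A block is an entry criterion for facet pain, lumbar or cervical (protocol 5.3.2.1: "achieving at least 50% pain relief, with real-time injection of radiographic contrast under fluoroscopic guidance"), and for sacroiliac pain (5.3.3.1, also at least 50% relief). The criteria for radicular, trigeminal, knee and hip pain name no block.

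Neither document gives a minimum time from block to baseline or says that the NRS recall period must be free of block effect. The visible SAP text does not address the point.

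**The concern.** The rule and the measurement cover different periods. Section 6.2 asks about the state of the subject when the question is put; the question itself asks about the day before. For example, a block is given at 9:00, its effect ends at 17:00, and baseline is taken at 9:00 the next day. The rule is met, yet 8 of the 24 recalled hours were under the block.

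The baseline NRS is the denominator of the primary endpoint and of both responder definitions. If block relief lowers it and the follow-up score is unaffected, measured improvement shrinks. Exposure depends on whether the indication uses a block and on how soon afterwards a site takes baseline, so the effect could differ by indication and by site. Section 5.1 plans about 20 subjects per indication, so one subject who falls below a responder cut-off moves that indication's proportion by 1/20 = 5 percentage points.

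**Working it through.** The plan states no figure on this point, so there is none to reproduce. The check has two parts.

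**Reading the sections together.** Section 6.2 is satisfied if the block effect has ended by the time of the assessment. Section 6.4.2.1 counts the preceding 24 hours. A block whose effect ended within those 24 hours satisfies the first and enters the second. No other visible passage closes the gap.

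**Size, as an illustration.** Inputs:
- B = pain without the block. An assumption; 8 is used below.
- r = relief while the block acts. 50% is the minimum in 5.3.2.1 and 5.3.3.1; 100% is shown as the upper end.
- h = hours of block effect inside the recall window. Not in the documents; assumed range 2 to 12.
- d = true relative reduction at follow-up. 50% is used, so follow-up pain is 4.
- Recall is assumed to be time-weighted, and relative change is read as (baseline − follow-up) / baseline.

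Recorded baseline = B × (1 − r × h/24).

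Measured reduction = 1 − (1 − d) / (1 − r × h/24). B cancels, so this does not depend on the starting pain level.

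| h | Recorded baseline, r = 50% | Measured reduction, r = 50% | Recorded baseline, r = 100% | Measured reduction, r = 100% |
|---|---|---|---|---|
| 0 | 8.00 | 50.0% | 8.00 | 50.0% |
| 2 | 7.67 | 47.8% | 7.33 | 45.5% |
| 4 | 7.33 | 45.5% | 6.67 | 40.0% |
| 8 | 6.67 | 40.0% | 5.33 | 25.0% |
| 12 | 6.00 | 33.3% | 4.00 | 0.0% |

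For h = 8 and r = 50%: 8 × (1 − 0.5 × 8/24) = 6.67, and 1 − 4/6.67 = 40.0%.

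**Whole-number scores.** Section 6.4.2.1 does not say whether the NRS is recorded in whole points. If it is, the r = 50% baselines for h = 2, 4, 8 and 12 become 8, 7, 7 and 6. The measured reductions are then 50%, 43%, 43% and 33%, so the shift vanishes at 2 hours and remains at 4 hours and above.

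**Group level.** If a share p of an indication's baselines is affected by the same h and r, the mean shift is p times the individual shift. For 4 to 12 hours at 50% relief that is p × 4.5 to p × 16.7 percentage points. The documents do not give p, and it may be zero.

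**The case against.** **Blocks probably come well before baseline.** Section 1.1.1 describes the block as preceding the recommendation for RFA. Section 3.2 screens patients already scheduled for RFA, and being scheduled is a general inclusion criterion. Sections 15.0 and 15.2 describe the study procedures as standard of care, with only questionnaires added. This stands as a limit on frequency: many baselines may be unaffected. It does not close the gap, because none of these sections sets an interval.

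**The intent of 6.2 is clear.** A careful site may apply the rule to the whole recall period without being told. That is a fair reading, but the text does not say so, and practice may vary between sites.

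**The timing rules might seem to force the problem.** Under 5.3, screening tests outside a site's standard set are done after consent. Under 5.4, enrollment needs "Subject has been determined to meet all Inclusion/Exclusion requirements", and 6.2 puts baseline on the day of enrollment. A reader might infer that, where the block is the last criterion to be met, the same-day rule collides with the rule on block effect. The documents do not support this. The provision in 5.3 is conditional, and on the protocol's own account the block is standard care. Nothing in 5.4 ties the eligibility determination to the day of the block. A site can enroll and take baseline together on a later day and satisfy both sentences of 6.2.

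**Responder losses can be overstated.** In the illustration the true reduction sits exactly on the 50% cut-off, so any downward shift in an unrounded baseline loses the responder. A subject with true pain 8, 4 block hours and follow-up pain 3 remains a responder: 1 − 3/7.33 = 59%. Only subjects near a cut-off change category.

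**Eligibility might also seem to be affected.** True pain 7 with 8 block hours at 50% relief gives 7 × (1 − 0.5 × 8/24) = 5.83, below the entry level of 6. If scores are whole numbers this becomes 6, and the criterion does not say which reading counts. The documents do not settle whether anyone would be wrongly excluded.

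**Conclusion.** The mismatch is in the text: a baseline taken in line with 6.2 can include hours of block relief. Where that happens, baseline pain, the relative change in NRS and the responder proportions are all understated. The indications mainly exposed are the three that require a block. Others are not ruled out, since 6.2 speaks of diagnostic blocks in general.

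The size cannot be determined from the documents. The range of 45.5% to 33.3% in place of a true 50% rests on 4 to 12 assumed block hours, the minimum qualifying relief and time-weighted recall. Greater relief would widen it, and an interval of days would remove it.

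A reader might infer that the primary conclusion is at risk. That does not follow. The bias makes the device look less effective, the hypothesis is tested against zero, and a reduction of 33% to 45% is still far from zero. What is affected is the accuracy of the estimates and responder rates by indication. This is a cheap improvement and does not point to a flaw in the test.

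**What to change.** In section 6.2, replace the phrase that ties the rule to the time of the assessment with wording such as: *No effect of a diagnostic block may fall within the 24-hour recall period of the baseline NRS.* With h = 0 the recorded baseline equals B and this bias is zero.

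Record the date and time of the last block at baseline, if the case report form does not already do so (the forms are held separately and could not be checked). A date alone cannot settle a case such as a block one morning and baseline the next.

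Keep the rule that baseline is taken on the day of enrollment, since both can be held once the condition is met. Do not add a requirement that pain has returned to its pre-block level: the first scheduled NRS is at baseline, so there would be nothing to compare it with.

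The cost is one amended sentence and at most one form entry. A few subjects would enroll and complete baseline a day or so later.
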